3.3.1.2 Exclusion Criteria

Patients who meet any of the following criteria will not be eligible to participate in the study:

- 1. Patient has a history of complete lack of GERD symptom response to PPIs.
- 2. Patient reports epigastric pain or epigastric burning as his or her predominant symptom at the Screening Visit.
- 3. Patient has a diagnosis of gastroparesis per gastric emptying study, or a history of bowel obstruction, or is at risk for a bowel obstruction (eg, patient has an organic gastrointestinal [GI] motility disorders or a history of major GI surgery).
- 4. Patient has a history of serum triglyceride concentrations > 500 mg/dL on a fasting specimen, or has serum triglyceride concentrations > 500 mg/dL on a fasting specimen at Screening or any time during the Pretreatment Period.
- 5. Patient has a history of hypertriglyceridemia-induced pancreatitis.
- 6. In the Investigator's opinion, patient is susceptible to a deficiency of fat-soluble vitamins (especially vitamin D deficiency; eg, the patient has osteoporosis or osteomalacia) and will be put at risk by receiving colesevelam for 8 weeks.
- 7. Patient has an active swallowing disorder that would compromise their ability to swallow the study medication.
- 8. Patient has any alarm symptoms including, but not limited to, GI bleeding, anemia, vomiting, or unexpected weight loss at any time during the Screening or Pretreatment Periods.
- 9. Patient has undergone surgery that meets any of the following criteria:
 - a. Surgery of the GI tract (including gastric banding) other than an appendectomy, cholecystectomy, or minor oral or rectal surgery (eg, tonsillectomy, hemorrhoidectomy, rectocele repair) at any time before the Screening Visit
 - b. An appendectomy during the 3 months before the Screening Visit, or a cholecystectomy during the 6 months before the Screening Visit, or minor oral or rectal surgery during the 30 days before the Screening Visit

- c. Non-GI surgery of the abdomen, pelvis, or retroperitoneal structures during the 6 months before the Screening Visit
- d. Thoracic surgery during the 6 months before the Screening Visit
- e. Other major non-GI surgery during the 30 days before the Screening Visit
- 10. Patient has previously undergone thoracic or abdominal radiotherapy.
- 11. Patient has large (>5 cm) hiatal hernia.
- 12. EGD, conducted during the Screening Period, reveals that the patient has long-segment Barrett's esophagus (greater than 3 centimeters) or definite dysplastic changes in the esophagus, peptic ulcer disease, active GI bleeding, presence of symptomatic esophageal strictures, presence of esophageal or fundic varices, erosive gastritis, or eosinophilic, herpetic or Candida esophagitis.
- 13. Patient has Gilbert's disease, Crohn's disease, diabetes mellitus (defined as A1C >6.5%), Zollinger-Ellison syndrome, pancreatitis, cholecystitis, or systemic sclerosis.
- 14. Patient has elevated (defined as > 1.5 times the upper limit of normal by the laboratory) levels of serum bilirubin at Screening.
- 15. Patient has a history of clinically significant hypersensitivity or allergies to any of the excipients contained in the study medication (active or placebo).
- 16. Patient has a history of cancer (resected basal cell or squamous cell carcinoma is acceptable). Note: patients with a history of cancer are allowed provided that the malignancy has been in complete remission for at least 5 years before the Screening Visit. A complete remission is defined as the disappearance of all signs of cancer in response to treatment.
- 17. Patient has active substance abuse or history of chronic substance abuse (including alcoholism but not including nicotine) within 12 months before the Screening Visit or is positive for any of the following at the Screening Visit unless legally prescribed for anything but gastrointestinal pain: amphetamines, benzodiazepines, opiates, barbiturates, cocaine, or phencyclidine.
 - Note: Marijuana use, whether prescribed or not, is prohibited from 30 days before screening through the duration of the study. Use of illicit drugs is not allowed during the study.
- 18. Patient has any clinically significant finding on a physical exam, 12-lead electrocardiogram (ECG), or clinical laboratory test after signing the ICF but before receiving the first dose of study medication. (Note: The Investigator will determine if a particular finding is clinically significant. In making this determination, the Investigator will consider whether the particular finding could prevent the patient from performing any of the protocol-specified assessments, could represent a condition that would exclude the patient from the study,

- could represent a safety concern if the patient participates in the study, or could confound the study-specified assessments of safety or efficacy.)
- 19. Patient reports using a prohibited medication during the Screening or Pretreatment Periods, or is not willing or able to abide by the restrictions regarding use of prohibited medications as defined in Appendix 4.
- 20. Patient has received an investigational drug during the 30 days before the Screening Visit, or is planning to receive another investigational drug or use an investigational device at any time during the study.
- 21. Patient has an acute or chronic condition that, in the Investigator's opinion, would limit the patient's ability to complete or participate in this clinical study.
- 22. Patient has previously entered the Treatment Period of an IW-3718 study.
- 23. Patient has previously entered the Pretreatment Period of this study. (Note: patients who failed the Pretreatment Period due to abnormal laboratory findings or timing issues may be re-screened.)
- 24. Patient is enrolled in this study at another clinical study site; is an employee of the Institution or Ironwood Pharmaceuticals; or is a first-degree family member, significant other, or relative residing with an employee of the Institution or Ironwood Pharmaceuticals.

3.3.2 Screening Failures

For all patients who are ineligible to participate in the trial, the reason for their screening failure will be recorded in the eCRF. Reasons for screening failure are as follows:

- Inclusion/Exclusion not met (specify)
- Protocol violation
- Withdrawal of consent
- Adverse event
- Lost to follow up
- Other (specify)

3.3.3 Removal of Patients from Therapy or Assessment

A premature discontinuation will occur when a patient who has signed the ICF ceases participation in the study, regardless of circumstances, before completion of the Treatment Period.

A patient will be considered to have completed the study after receiving 8 weeks of treatment and completing the End-of-treatment (EOT) Visit at Day 57. A window of +3 days will be allowed for the EOT visit; if a patient completes the EOT Visit prior to Day 57, this will be considered a protocol deviation.

Patients will be informed that they are free to withdraw from the study at any time and for any reason. The Investigator may remove a patient from the study if, in the Investigator's opinion, it is not in the best interest of the patient to continue the study. Patients may also be discontinued from the study by the Investigator or the Sponsor at any time for any reason, including the following:

- Adverse event(s)
- Non-compliance with study drug
- Protocol violation
- Withdrawal of consent
- Symptomatic deterioration
- Lost to follow-up (Note: every effort must be made to contact the patient; a certified letter must be sent.)
- Study termination by the Sponsor
- Physician decision
- Randomized in error
- Other reasons

The date the patient is withdrawn from the study and the reason for discontinuation will be recorded on the study termination form of the electronic case report form (eCRF). Randomized patients who discontinue from the study for any reason should complete the assessments required at the EOT Visit at the time of their discontinuation. Study centers should make a reasonable effort to follow any pregnant patients until delivery or end of the pregnancy.

If a patient does not return for a scheduled visit, the study center should contact the patient. An effort must be made to contact the patient, including sending a certified letter. In every case, the patient outcome, including lost to follow-up information, will be documented.

3.3.4 Replacement Procedures

Patients in this study who prematurely discontinue treatment will not be replaced.

3.4 STUDY TREATMENTS

3.4.1 Investigational Product

3.4.1.1 IW-3718

Study medication will be provided as 500 mg IW-3718 tablets which are light blue-green, oval shaped, film-coated tablets intended for oral administration. In addition to the active drug substance, colesevelam, 500 mg IW-3718 tablets contain the following inactive ingredients: microcrystalline cellulose, polyethylene oxide, colloidal silicon oxide, butylated hydroxytoluene, magnesium stearate, polyvinyl alcohol, polyethylene glycol, titanium dioxide, talc, FD&C Blue #1, and iron oxide yellow. Tablets should be taken whole and never broken, crushed, or chewed.

Patients randomized to receive IW-3718 will self-administer the three 500 mg IW-3718 tablets BID, immediately after the morning and evening meals.

3.4.1.2 Placebo

Placebo to match 500 mg IW-3718 tablets will be provided as light blue-green, oval shaped, film-coated, oral tablets containing microcrystalline cellulose, polyethylene oxide, colloidal silicon oxide, butylated hydroxytoluene, magnesium stearate, polyvinyl alcohol, polyethylene glycol, titanium dioxide, talc, FD&C Blue #1, and iron oxide yellow. Tablets should be taken whole and never broken, crushed, or chewed.

Patients randomized to receive placebo will self-administer the three placebo tablets BID immediately after the morning and evening meals.

3.4.1.3 Rescue Medicine

Antacid rescue medicine will be provided to patients as a bottled liquid (magnesium hydroxide 200 mg/aluminum hydroxide 200 mg per 5 mL).

During completion of the nighttime eDiary questions, patients will be asked about their rescue medicine use by responding to the following questions:

• "How many times did you use your rescue medicine (liquid antacid) during the past 24 hours?"

3.4.1.4 Treatment Adherence

Patients will be dispensed the appropriate number of Sponsor-packaged, labeled bottles containing 210 tablets needed until the next study visit (see Section 3.6). Patients will be asked to return all bottles (including unused tablets) at each study visit for assessment of compliance with the dosing regimen.

Patients will record their PPI administration each day (once daily) in their eDiary.

3.4.2 Packaging and Labeling

Study medication (IW-3718 and placebo tablets) will be provided by Ironwood as 210-count bottles. Study medication will be uniquely numbered and labeled in a double-blind fashion that conforms to regulatory requirements.

3.4.3 Storage and Stability

IW-3718 tablets and matching placebo will be shipped at controlled room temperature between 15°C and 25°C (59°F and 77°F) and must be stored at room temperature between 20°C and 25°C (68°F and 77°F); excursions are permitted between 15°C to 30°C (59°F to 86°F).

Any deviation from these storage conditions must be reported to Ironwood and use of the study medication suspended until authorization for its continued use has been provided by Ironwood.

The Investigator must ensure that the receipt and use of all study medication supplied is recorded and must supervise the storage and allocation of these supplies. All study medication supplies must be retained in a locked room that may only be accessed by the Investigator, or other duly designated persons. Study medication must not be used outside the context of this protocol, and under no circumstances should the Investigator or study center personnel allow the supplies to be used other than as directed by this protocol without prior authorization from Ironwood.

Antacid rescue medicine (aluminum hydroxide/ magnesium hydroxide liquid) will be supplied by the clinical sites and stored in accordance with the manufacturer's instructions.

3.4.4 Method of Assigning Patients to Treatment Groups

Eligible patients will be stratified by whether they have or do not have erosive esophagitis on the screening EGD, and by their baseline WHSS (<3 vs. ≥3), and then randomized through central randomization in a 1:1 ratio to receive either 1500 mg IW-3718 BID or placebo BID, both administered in addition to the patient's per-label QD PPI therapy.

The computer-generated randomization schedule will be prepared by an independent statistician not otherwise associated with the study.

3.4.5 Selection of Dosage in the Study

During this study, an oral dose of 1500 mg IW-3718 BID (total daily dose of 3000 mg/day) given as an adjunct to QD PPI for 56 days, will be studied to evaluate the safety and efficacy of IW-3718 in a placebo-controlled study. Dose reductions are not permitted. This dose was selected for Phase 3 evaluation based on the results of Phase 2b Study ICP-3718-202. In that dose-ranging study, which evaluated IW-3718 doses of 500 mg, 1000 mg, and 1500 mg BID compared with placebo, dose-dependent improvement compared with placebo was observed for the primary endpoint, percent change from baseline in heartburn severity at Week 8. The 1500 mg dose showed an improvement in heartburn severity from baseline of -58.0 compared with a placebo improvement of -46.0 (nominal p-value = 0.04). Percent change from baseline in regurgitation frequency score at Week 8 was also significantly improved for IW-3718 1500 mg (-55.4) versus placebo (-37.9) (nominal p=0.01). Additional improvement for IW-3718 1500 mg relative to the IW-3718 500 mg and 1000 mg doses when compared with placebo were noted for other endpoints, including the heartburn and regurgitation responder endpoints; greater improvement was also noted for the IW-3718 1500 mg dose group within the EE subpopulation. IW-3718 1500 mg was generally well-tolerated in Study ICP-3718-202. The incidence of TEAEs for the IW-3718 1500 mg group (44.1%) was comparable to the overall IW-3718 incidence (46.2%) and to placebo (41.4%). There was a dose-related trend in the incidence of patients who had nausea (2.9%, 4.2%, 5.6%, and 8.8% of patients in the placebo, 500-mg, 1000-mg, and 1500-mg IW-3718 groups, respectively). Otherwise, no dose-related trends were noted for any TEAEs.

3.4.6 Selection and Timing of Dose for Each Patient

Patients will be randomized to receive 1500 mg IW-3718 BID or placebo BID. The first dose of study medication will be taken with liquid and a snack in clinic at the Randomization Visit (on Day 1). Patients should take their second dose that evening immediately upon completion of dinner, ensuring that at least 8 hours have elapsed since the first dose in clinic.

During the Treatment Period, patients will take study medication BID at home, in the morning (immediately upon completion of breakfast) and in the evening (immediately upon completion of dinner), even on study visit days. The last dose of study medication will be taken the morning of the EOT Visit.

Additionally, all patients will take their current PPI during the Pretreatment, Randomization, and Treatment Periods (ie, Day -21 through Day 57 [+ 3 days]). The PPI will be taken each day, approximately 30-60 minutes before breakfast.

During completion of the daily eDiary questions, patients will be asked to confirm daily dosing of their PPI by responding to the following question:

• "Did you take your PPI this morning?"

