1.2 IW-3718

Ironwood is developing IW-3718 as an adjunct to PPI therapy for treatment of persistent GERD (also referred to as refractory GERD) in patients whose heartburn and regurgitation symptoms are not resolved with PPI therapy alone. IW-3718 is a sustained-release engineered form of colesevelam hydrochloride (henceforth referred to as colesevelam), a bile acid sequestrant.

IW-3718 tablets are formulated as an extended-release, solid, oral-dosage form intended to extend the release of colesevelam into the stomach. As a result of the sustained release, colesevelam binds to the bile acids that are refluxed into the stomach and upper duodenum, forming a bile acid-colesevelam complex and preventing the free bile acids from entering the esophagus. Subsequently the bile acid-colesevelam complex will travel down the GI tract and be excreted without being absorbed.

The extended-release formulation in IW-3718 tablets is based on Assertio's Acuform® technology which utilizes swelling polymers to allow the tablet to be retained in the stomach for up to approximately 9 hours when dosed in the fed state, during which time the tablet slowly releases the active ingredient in the stomach and upper GI tract. The tablet's active ingredient is steadily released in the stomach and upper GI tract in a near zero-order manner. It's theorized that the resulting sustained levels of colesevelam in the stomach will prevent bile acids from refluxing into the esophagus. The Acuform technology is well-characterized, and currently utilized in several Food and Drug Administration (FDA)-approved drugs such as Glumetza® (metformin HCl, extended release), Proquin® XR (ciprofloxacin HCl monohydrate, extended release), and Gralise™ once-daily (gabapentin) tablets.

Colesevelam is an orally administered, non-absorbed, non-digestible polymer that binds bile acids in the GI tract. Colesevelam was initially approved in 2000 in the United States (US) as the active ingredient in WelcholTM and indicated 1) as an adjunct to diet and exercise for reduction of elevated low-density lipoprotein cholesterol (LDL-C) in adults with primary hyperlipidemia (as monotherapy or in combination with statin therapy), 2) to reduce LDL-C levels in boys and postmenarchal girls, 10 to 17 years of age, with heterozygous familial hypercholesterolemia as

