3.5.8 Other Assessments

3.5.8.1 Esophagogastroduodenoscopy

All patients will be required to undergo an EGD during the Screening Period. There should be a minimum of 7 days between the EGD and the start of the Pretreatment Period to allow for pH testing and patient stabilization. EGDs will be interpreted by the local site personnel and by a central reader. Details are provided in a separate study manual (Image Acquisition Guidelines for Ironwood Pharmaceuticals, Inc. Protocols C3718-301/C3718-302; WorldCare Clinical).

An EGD will be performed at the Week 8 / EOT Visit in all patients who completed at least 4 weeks of treatment and had erosive esophagitis on the EGD obtained during the Screening Period (based on the Los Angeles [LA] classification of esophagitis [Appendix 5], as determined by either the site personnel or the central reader).

3.5.8.2 **Bravo**TM

At all sites, all patients will undergo up to 96 hours of pH testing with the Bravo device. If for some reason 96 hours of testing is not possible, then approximately 48 hours of testing is acceptable. All patients will return to the site with their Bravo pH monitor after approximately 96 hours (or 48 hours where applicable) to return the recording device. To determine eligibility, a centralized review of pH monitoring will be conducted for each patient. Please refer to the Bravo Site Manual for specific instructions.

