3.6.2 Treatment Period (Day 1 to Day 57)

For all visits during the Treatment Period, patients will take their PPI and study medication (except for the Randomization Visit) prior to reporting to the study site.

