3.6.2.3 Week 8/End-of-treatment (Visit 5) Procedures

- Register visit in IWRS
- Physical examination
- Body weight
- EGD (A repeat EGD will be performed at the Week 8 / EOT Visit for all patients who have completed at least 4 weeks of treatment and had erosive esophagitis on the screening EGD [based on the LA classification of esophagitis, see Appendix 5] as determined by either the site personnel or the central reader; see Section 3.5.8.1)
- Seated vital signs
- 12-lead ECG
- Concomitant medications and procedures
- Collection of blood and urine samples for clinical laboratory tests, including:

Clinical chemistry

Hematology (CBC)

Coagulation

Urinalysis

- Pregnancy test for all female patients of childbearing potential (must be confirmed negative; positive urine test results will be confirmed via serum pregnancy test)
- AE evaluation (throughout the Treatment Period)
- Review eDiary
- WPAI-Sleep Disturbance-GERD
- EQ-5D-3L
- Return of all unused study medication
- Return eDiary

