3.6.4 Early Termination Procedures

Patients who discontinue from the study for any reason should complete the assessments required at the EOT Visit (Section 3.6.2.3) at the time of their discontinuation.

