3.8 CHANGES IN THE CONDUCT OF THE STUDY OR PLANNED ANALYSES

Any amendment to this protocol will be provided to the Investigator in writing by Ironwood or its designee. Prior to implementation, any protocol amendment regarding reportable deviations (as defined by the IRB/IEC) must be approved by the IRB/IEC and the signature page must be signed by the Investigator and received by Ironwood or its designee, with the following exception: If the protocol is amended to eliminate or reduce the risk to patients, the amendment may be implemented before IRB/IEC review and approval. However, the IRB/IEC must be informed in writing of such an amendment, and approval must be obtained within reasonable time limits.

Deviating from the protocol is permitted only if absolutely necessary for the safety of the patients and must immediately be reported to Ironwood or its designee.

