- k. For all female patients of childbearing potential, a negative urine or serum pregnancy test must be performed and documented at the Screening Visit, and at the Randomization Visit (before dosing) in order for the patient to be randomized into the study. A urine or serum pregnancy test will also be obtained at the Week 4 and EOT Visits. All positive urine pregnancy test results will be confirmed by a serum pregnancy test.
- 1. Patients must undergo a urine drug screen for selected drugs of abuse (cocaine, barbiturates, amphetamines, opiates, benzodiazepines, and cannabinoids) and a serum alcohol screen at the Screening Visit.
- m. For randomized patients, all AEs will be captured from the time the patient signs the ICF through the Follow-up Phone call.
- n. Rescue medicine (aluminum hydroxide / magnesium hydroxide) will be supplied to patients at the Pretreatment Visit, and if needed, at subsequent visits.
- o. The eDiary will be dispensed at the Pretreatment Visit. Patients must complete daily questions at least 5 days each week during the 14 days before the Treatment Period and must complete the weekly questions at least once during the 7 days before the Treatment Period in order to be eligible for randomization. Patients should bring their eDiary to each visit. The eDiary will be used for daily assessments (PPI administration, mRESQ-eD, dyspepsia symptoms, sleep disturbance, and rescue medication use), and weekly assessments (degree of relief, symptom bothersomeness, symptom relief, treatment satisfaction, and questionnaires).
- p. The first dose of study medication will be administered in the clinic with liquid and a snack at the Randomization Visit. At all other visits, patients will take study medication prior to arriving at the clinic but will be dispensed additional doses needed until the next study visit.
- q. Treatment adherence with study drug will be assessed based on return of unused tablets.
- r. Study site will contact each patient via telephone 7 days after the EOT Visit to collect information pertaining to ongoing AEs/SAEs/concomitant medications/concomitant therapies, and information concerning any new AEs/SAEs /concomitant medications/concomitant therapies since the EOT Visit.

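### The dosing text puts breakfast and three tablets before the end-of-treatment endoscopy, and SAP 7.9 read literally drops that endoscopy if the last dose fell on an earlier day

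*Protocol*

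**What the plan says.** **Dosing.** Protocol 3.4.6 places the morning dose directly after breakfast, study visit days included, and adds: "The last dose of study medication will be taken the morning of the EOT Visit". Protocol 3.6.2 says that at Treatment Period visits "patients will take their PPI and study medication (except for the Randomization Visit) prior to reporting to the study site". SAP Appendix 4, note p, repeats the rule: "At all other visits, patients will take study medication prior to arriving at the clinic". Each dose is three tablets in both arms (Protocol 3.4.1.1 and 3.4.1.2). Protocol 1.2 describes the IW-3718 formulation as designed to "allow the tablet to be retained in the stomach for up to approximately 9 hours when dosed in the fed state"; no figure is given for placebo.

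**Endoscopy.** Protocol 3.6.2.3 says "A repeat EGD will be performed at the Week 8 / EOT Visit for all patients" who had EE at screening and at least 4 weeks of treatment. Under Protocol 3.6.4, patients who leave early "should complete the assessments required at the EOT Visit (Section 3.6.2.3) at the time of their discontinuation". On how the EGD is done and read, Protocol 3.5.8.1 says "Details are provided in a separate study manual".

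**Departures.** Protocol 3.8 states: "Deviating from the protocol is permitted only if absolutely necessary for the safety of the patients". Any deviation must be reported at once.

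**Analysis.** SAP 5.2.3 lists EE healing, taken from the EGD, among the other efficacy assessments. SAP 7.9 leaves out any efficacy measurement dated later than the last dose and makes no exception for the EGD. EE healed and EE improved by at least one grade are exploratory items 16 and 17 in SAP Table 7.

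**The concern.** Read together, the rules send a patient to endoscopy having just eaten and swallowed three tablets which, on active drug, are meant to stay in the fed stomach for hours. If the procedure calls for an empty stomach, the protocol as written works against patient safety and image quality. A site that protects the patient by withholding food and drug has to record a deviation.

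The SAP adds a second problem. A site that skips the morning dose moves the last dose to the evening before, and the EGD then falls on the wrong side of the SAP 7.9 cut-off. The same happens to a patient who stopped treatment after at least 4 weeks and is scoped on a later day. In both cases the data lost would be the EE healing and improvement results.

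**Working it through.** The plan gives no figure to reproduce on this point. The check is a reading of the rules, a date comparison and a count.

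**1. Is there a dose on the EOT morning?** Yes, on three consistent statements: Protocol 3.4.6, Protocol 3.6.2 and SAP Appendix 4 note p. The tablet count in SAP 7.4.1 agrees: it takes 6 per day and subtracts 3 when counting ends on the EOT Visit day. For Day 57 that is 57 × 6 − 3 = 339, which leaves one dose for that morning.

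**2. What can a site do, and what does SAP 7.9 then do?** The literal rule keeps the EGD only if EGD day ≤ last dose day. For an EOT Visit on any of Days 57 to 60:

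| Handling of the EGD morning | Protocol | Last dose day | EGD in items 16 and 17 |
|---|---|---|---|
| Breakfast and dose as written | followed, patient fed | EGD day | kept |
| Dose given after the EGD, same day | departs from 3.6.2 | EGD day | kept |
| Dose skipped | departs from 3.4.6 and 3.6.2 | EGD day − 1 | dropped |
| Treatment stopped earlier (after ≥ 4 weeks), EGD on a later day | 3.6.4 applies | before EGD day | dropped |

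**3. How many patients are due a repeat EGD?** Inputs: N = 550 (SAP 3.4) or 660 (Protocol 3.3 and SAP 4); EE share 45% (SAP 4) or 50% (the upper aim in Protocol 3.3); about 10% discontinuing, as in Study ICP-3718-202 (SAP Appendix 1).

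- Completers, low: 550 × 0.45 × 0.90 = 222.8, about 223.
- Completers, high: 660 × 0.50 × 0.90 = 297.
- With 1:1 allocation, about half (111 to 149) take the active tablets, the only ones with a stated retention time. The breakfast instruction applies to both arms.
- Discontinuers with EE: at most 660 × 0.50 × 0.10 = 33 if all leave after Week 4, and 0 if all leave before.

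Patients with EE on the central read only would add a number the documents do not give.

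**4. Are the confirmatory endpoints touched?** No. The heartburn and regurgitation items are answered in the evening. The Week 8 window closes on Day 56 (SAP Table 15), and on the EOT Visit day only the morning diary is expected (SAP 7.4.2). Moving the last dose from the EOT morning to the evening before therefore removes no score from the primary or key secondary endpoints.

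**5. Can new dosing text still reach the mITT patients?** The last mITT patient was randomized no later than 4 August 2020 (SAP 7.1). Day 60, the end of the EOT window, is 59 days on: 2 October 2020. The SAP is dated 14 January 2021. For mITT EGDs, only the SAP wording can still be changed.

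**The case against.** **Fasting is not in the documents.** No supplied text says an EGD needs an empty stomach, and without that assumption dose and EGD coexist and the EGD is kept. Preparation may be in the imaging manual, and the protocol is equally silent on fasting for the screening EGD. This stands as a limit: the documents do not show that preparation was overlooked or that patients were scoped unsafely. It does not remove the point, because a fasting line in the manual would contradict Protocol 3.4.6 and 3.6.2 and leave SAP 7.9 unchanged.

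**The dosing text is less uniform than it looks.** Protocol 3.1 has medication stopped at the end of treatment with patients then returning for the EOT Visit, and 3.4.5 speaks of 56 days. These are looser statements; the specific ones (3.4.6, 3.6.2, note p) and the SAP 7.4.1 count all put a dose on the EOT morning.

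**The SAP 7.9 cut-off may be meant for diary data.** The sentence closes a paragraph on diary responder rules and period averages. The footnotes to SAP Tables 15 and 16 state a matching rule for diary windows and keep later values for the sensitivity analysis. That is a reasonable guess at intent. But the sentence covers efficacy assessments without limit, SAP 5.2.3 counts the EGD among them, and those footnotes sit under diary tables and do not clearly extend to the EGD.

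**The counts are eligibility, not loss.** This is correct. A reader might infer that 223 to 297 healing results will disappear. The documents do not support that: an EGD drops out only if the last dose fell on an earlier day, and how often that happens is not known.

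**Conclusion.** The point holds as a minor one. The protocol and SAP require food and three tablets before the visit that carries the repeat EGD and make no exception. On the assumption that endoscopy is done fasted, a site must scope a fed patient or deviate. Protocol 3.8 may permit the deviation on safety grounds, but a foreseeable situation in some 223 to 297 completers should not depend on it.

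The data consequence is narrower. Literal SAP 7.9 excludes the EGD only where the last dose precedes the EGD day; dosing as written, or after the EGD on the same day, keeps it. The number lost could be zero. Only exploratory items 16 and 17 are exposed, and they lie outside multiplicity control.

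Two stronger inferences are not supported: that withholding the dose in any form loses the EGD, and that the primary or key secondary results are at risk. The conclusion rests on the fasting assumption, on the imaging manual being unseen, and on a literal reading of SAP 7.9.

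**What to change.** **(a) Dosing text.** In Protocol 3.4.6 and 3.6.2, and in SAP Appendix 4 note p, state that patients having a repeat EGD omit breakfast and the morning study dose until after the procedure, or take their last dose the evening before. State also that this is not a deviation, and whether the PPI, which 3.6.2 also places before arrival, is taken that morning. This helps only patients whose EOT Visit is still to come.

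**(b) SAP 7.9.** Before unblinding, add one sentence: the protocol-scheduled EOT or early-termination EGD is not subject to the last-dose-date cut-off. It is needed alongside (a), because taking the last dose the evening before would otherwise itself exclude the EGD. A plain exemption is better than a 1-day allowance, which would still drop early terminators scoped later than that.

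**Cost.** A few lines of protocol text, a site letter and one SAP sentence; no added visit or procedure. At most one final dose is lost for a Day 57 visit: 56 × 2 = 112 doses instead of 113, after the Week 8 diary window has closed. Adverse events on the EGD day stay within 1 day of the last dose and so still count as treatment-emergent (SAP 7.10.1). Some early-termination EGDs will be read a few days off drug. SAP 7.4.1 needs no change if the count runs to the last dosing day: ending on Day 56 gives 56 × 6 = 336 tablets.
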